## Safety considerations and participant insurance

No adverse event are to be expect. The participants will be instructed by the principal investigator on treadmill walking and the safety system. The safety system will consist of a safety harness that will be attached to a suspension system, two handrails, light gates at the front and back of the belt and an emergency button at the operating desk. The participants will have five minutes of familiarization with the treadmill operated with matched walking speed from the level walking trials. All participants will be insured by a clinical trial insurance.

## Examination Procedures

At first, height will be measured with a stadiometer to the nearest 0.5 cm (SECA 213), and weight with a medical scale (Marsden M-420). Furthermore, joint range of motion and functional hamstring flexibility will be assessed. Thereafter, all participants will be equipped with 43 retroreflective markers on bony landmarks and 16 markers on four rigid clusters on thighs and shanks. Five level walking trials will be captured to evaluate if gait pattern is physiological or not. Participants will have to walk on a five-meter ramp with 10° inclination which is equipped with 24 infrared cameras (Vicon, Oxford, United Kingdom) and two force plates (Kistler, Winterthur, Switzerland). After seven left and seven right foot strikes on

the force plates for up and down walking each, the participants will be guided to the Gait Real-time Analysis Interactive Lab (GRAIL, Motekforce Link, Amsterdam, Netherlands), which is located next door. The GRAIL is a dual-belt treadmill equipped with two force plates, a 180° virtual reality screen and a motion capturing system with ten infrared cameras. After the familiarization phase on the treadmill with an inclination of 10° and with matched speed of incline walking, three times a period of 20 seconds will be recorded within 3 minutes. The investigator will explain the self-paced mode of the treadmill to the participant afterwards. The self-paced mode will adapt the belt speed automatically based on the position of the participant on the treadmill. Following a familiarization phase, data will be recorded as before.

This procedure will be repeated on the treadmill with a declination of 10°. Thereafter, the three following tasks will be performed in the order as specified in the sequence list.

#### *Self-paced decline walking*

The participants will be instructed to walk on the declined treadmill with self-selected speed. They will complete a five-minute familiarization period and a three-minute measurement period. Within the measurement phases, three times a period of 20 seconds of self-paced walking will be recorded.

#### *Self-paced decline walking with internal focus of attention*

The participants will be instructed to walk on the declined treadmill with self-selected speed. During walking, they will have to concentrate on an internal focus of attention, as keeping their spine as long towards the ceiling as possible. The participants will complete a five-minute familiarization period and a three-minute measurement period. In the measurement phase, three times a period of 20 seconds of self-paced walking

#### *Self-paced decline walking with real-time feedback, followed by speed-matched decline walking*

The participants will be instructed to walk on the declined treadmill with self-selected speed. During walking, they will have to concentrate on specific real-time feedback presented on the projection screen. This feedback visualization will represent the simplified frontal knee alignment movement using the participants knee position in relation to the ankle. The participants will complete a five-minute familiarization period and a three-minute measurement period. In the measurement phases, three times a period of 20 seconds of self-paced walking will be recorded. After this task, a control trial will take place with matched speed and without any feedback instruction.

## **Ethical and data protection aspects**

This study will be submitted to the ethics committee of the Medical University of Vienna. With respect to participating students, there is a teacher-student relationship between

researcher and participants. Besides general ethical principles, i.e. voluntary participation, data protection and confidentiality, provision of contact details of the research team, it will be emphasized in the course of obtaining informed consent, that refusing or withdrawing consent will not have any consequences on the remaining academic education. Participants will be assigned a continuous study code (UD01 – UD30) to protect identifiable data. The assignment key will be locked in the study manager office, separate from identifiable study data.

## Outcome parameters

Height, bodyweight and inter-anterior superior iliac spine distance will be measured at the beginning of all sessions. Furthermore, flexibility of hamstrings and triceps surae will be assessed clinically. The primary outcome of this study is the frontal knee range of motion during the stance phase. Stance phase will be defined between heel-strike and toe-off of the observed leg. A second focus is on the ground reaction force loading ratio. Thirdly, the kinematics for the sagittal, frontal and transversal plane for hip, knee and ankle and the external moments for the sagittal and frontal plane for hip, knee and ankle will be assessed as well as step time, step length, step width, cadence and walking speed (table 1).

Area	Outcome Measure
Kinematic	3 planes of hip angle range of motion (°)
	Minimum sagittal hip angle (°)
	Maximum sagittal hip angle (°)
	3 planes of knee angle range of motion (°)
	Minimum sagittal knee angle (°)
	Maximum sagittal knee angle (°)
	Sagittal ankle angle range of motion(°)
	Minimum sagittal ankle angle(°)
	Maximum sagittal ankle angle(°)
	3 planes of pelvis angle range of motion (°)
	3 planes of trunk angle range of motion (°)
	Minimum sagittal trunk angle (°)
	Minimum sagittal trunk angle (°)
Kinetics	First peak load (N)
	Moment of first peak load (%)
	Average loading rate (N s  )
	Maximum loading rate (N sec  )
	Knee joint forces (N/kg)
	3 planes of minimum of hip external moments (Nm/kg)
	3 planes of maximum of hip external moments (Nm/kg)
	3 planes of minimum of knee external moments (Nm/kg)
	3 planes of maximum of knee external moments (Nm/kg)
	Minimum of sagittal ankle external moment (Nm/kg)
	Maximum of sagittal ankle external moment (Nm/kg)

Area	Outcome Measure
	Frontal knee abduction moment impulse (Nm/kg s)
	Frontal knee adduction moment impulse (Nm/kg s)
Spatio-temporal parameters	Walking velocity (m sec  )
	Cadence (steps min  )
	Step length (m)
	Step width (m)
	Stance phase duration (% gait cycle)
	Swing phase duration (% gait cycle)

**Table 1:** List of tertiary outcome parameters

Kinematic data will be time normalized from heel strike to heel strike, kinetic data from heel strike to toe-off. Individual participant data will be expressed as average per condition. Time normalization, data processing and parameter calculations will be done with self-developed scripts in MATLAB 2018a (The Mathworks, Natick, MA, USA).

## Statistical analysis

All metric parameters will be analyzed with SPSS 26 (IBM Corporation, Armonk, NY, USA). Data will be tested for normality using the Shapiro-Wilk Test, and graphical inspections of Q-Q-plots. Differences between ramp-walking and matched speed / self-paced walking on the inclined / declined treadmill will be analyzed using paired two-tailed t-test and tested for agreement using ICC [3.1, absolute agreement, single measures] with SEM of the ICC. To evaluate differences between the four conditions (decline walking, internal focus of attention, real-time feedback, and matched speed walking), a one-factorial analysis of variance with repeated measures will be used. Contrasts will be employed to test aforementioned pre-specified hypotheses. In view of the legitimization given with the hypothesis, two-sided testing will be applied. One-dimensional statistical parameter mapping (1dSPM) will be used to examine the steady parameters of the gait analysis. All other statistical tests than those related to the primary and secondary hypotheses are considered exploratory and statistical testing will be limited to tests as pre-specified by the hypotheses. Consequently, Bonferroni-Holm method will be used in terms of correcting for multiple testing. Alpha will be set to 0.05; exact p-values will be reported though.

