## Study goals and objectives

This cross-sectional observation of decline walking under four conditions, aims at enhancing the understanding of the effects of real-time feedback on lower limb gait kinematics and kinetics. Furthermore, the agreement of kinematic and kinetic parameters of 10° decline and incline walking between ramp and treadmill will be assessed.

The primary research question is, whether real-time feedback alters the frontal knee range of motion when compared to self-paced walking on the one hand, and matched speed walking on the other hand. The secondary aspect focuses on the effect of lower limb loading in decline walking. Thirdly, parameters of interest will be compared between declined/inclined ramp and declined/inclined treadmill walking. Consequently, underlying hypotheses were phrased as follows:

Primary null hypothesis: Means of the outcome "frontal knee range of motion" are equal across the four conditions a) self-paced walking, b) self-paced walking with internal focus of attention, c) self-paced walking with real-time feedback, and d) condition c speed-matched walking. Predefined contrasts hypothesize that:

- 1) The outcome of self-paced walking with internal focus of attention and self-paced walking with real-time feedback is equal to speed matched walking ( $bc=d$ )
- 2) The outcome of self-paced walking with internal focus of attention and self-paced walking with real-time feedback is equal to self-paced walking ( $bc=a$ )
- 3) The outcome of self-paced walking with real-time feedback is equal to self-paced walking with internal focus of attention ( $c=b$ )

Primary alternative hypothesis: Means of the outcome "frontal knee range of motion" are NOT equal across the four conditions a) self-paced walking, b) self-paced walking with internal focus of attention, c) self-paced walking with real-time feedback, and d) condition c speed-matched walking. Two-sided testing will be applied, as knowledge from existing literature is only moderate. Predefined contrasts hypothesize that:

- 1) The outcome of self-paced walking with internal focus of attention and self-paced walking with real-time feedback is NOT equal to speed matched walking ( $bc \neq d$ )
- 2) The outcome of self-paced walking with internal focus of attention and self-paced walking with real-time feedback is NOT equal to self-paced walking ( $bc \neq a$ )

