- 3) The outcome of self-paced walking with real-time feedback is NOT equal to self-paced walking with internal focus of attention ( $c < b$ )

Secondary null hypothesis: Means of the outcome "ground reaction force loading rate" are equal across the four conditions a) self-paced walking, b) self-paced walking with internal focus of attention, c) self-paced walking with real-time feedback, and d) condition c speed-matched walking. Predefined contrasts are for this outcome concordant with those of the primary hypothesis.

Secondary alternative hypothesis: Means of the outcome "ground reaction force loading rate" are NOT equal across the four conditions a) self-paced walking, b) self-paced walking with internal focus of attention, c) self-paced walking with real-time feedback, and d) condition c speed-matched walking. Two-sided testing will be applied, as knowledge from existing literature is only moderate. Predefined contrasts are for this outcome concordant with those of the primary hypothesis.

Tertiary null hypothesis:

- 1) The agreement of continuous kinematic and kinetic outcomes of the lower limb (see list of outcome parameters) between decline ramp walking and speed-matched decline treadmill walking is lower than 0.75 (ICC).
- 2) The agreement of continuous kinematic and kinetic outcomes of the lower limb (see list of outcome parameters) between decline ramp walking and self-paced decline treadmill walking is lower than 0.75 (ICC).
- 3) The agreement of continuous kinematic and kinetic outcomes of the lower limb (see list of outcome parameters) between incline ramp walking and speed-matched incline treadmill walking is lower than 0.75 (ICC).
- 4) The agreement of continuous kinematic and kinetic outcomes of the lower limb (see list of outcome parameters) between incline ramp walking and self-paced incline treadmill walking is lower than 0.75 (ICC).

Tertiary alternative hypothesis:

[figure not shown]
- 1) The agreement of continuous kinematic and kinetic outcomes of the lower limb (see list of outcome parameters) between decline ramp walking and speed-matched decline treadmill walking is at least 0.75 (ICC).
- 2) The agreement of continuous kinematic and kinetic outcomes of the lower limb (see list of outcome parameters) between decline ramp walking and self-paced decline treadmill walking is at least 0.75 (ICC).

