**Figure: Flow diagram of the progress through the phases of the trial**

## Sample size estimation and study population

As knowledge and studies concerning the effect of real-time feedback during decline walking is missing, sample size calculation based on proven effects is not applicable. Therefore sample size was arbitrary estimated with 25 based on the number of participants included in topic-specific studies, ranging from 14 to 40. Taking into account a drop out of 20% we will recruit 30 participants.

Those healthy participants will be included, according to the following inclusion criteria: 1) age from 18-35 years, 2) body mass index from 18.5 to 29.99 kg/m^2, 3) no chronological joint diseases and/or OA surgery, and 4) no neuro-motor diseases. Participants will be excluded from the analysis in case of 1) non-physiological and non-symmetrical gait patterns, and 2) severe outliers (more than two standard deviations).

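### Ramp-treadmill agreement is judged only by an ICC of at least 0.75, which scales the set-up difference by participant spread, and no acceptable difference in outcome units is set

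*Combined protocol and SAP*

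**What the plan says.** Study goals and objectives states as an aim that "the agreement of kinematic and kinetic parameters of 10° decline and incline walking between ramp and treadmill will be assessed". The same section turns this into four tertiary hypotheses: decline and incline, each with speed-matched and self-paced treadmill walking. The first null is that agreement "between decline ramp walking and speed-matched decline treadmill walking is lower than 0.75 (ICC"). Each alternative is an ICC of 0.75 or more, in the form "is at least 0.75 (ICC"). The hypotheses cover the continuous kinematic and kinetic lower-limb outcomes and point to the outcome list (Table 1).

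Statistical analysis has ramp-treadmill differences examined by a two-tailed paired t-test and "tested for agreement using ICC [3.1, absolute agreement, single measures] with SEM of the ICC". It sets no limit for the SEM, no acceptable difference in any outcome's units and no limits of agreement. It labels every test outside the primary and secondary hypotheses exploratory.

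Sample size estimation and study population restricts entry to healthy people, with "age from 18-35 years, 2) body mass index from 18.5 to 29.99" kg/m². It also removes from the analysis non-physiological and non-symmetrical gait and values beyond two standard deviations, without naming the variable. The limitations section notes that ramp and treadmill use different force plates and expects a possible small systematic error in the kinetic outcomes.

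**The concern.** The question is whether ramp and treadmill give the same values. A reader wants that in degrees, N or Nm/kg. The ICC instead gives the share of total variance that lies between people. If participants are alike on a parameter, a small set-up difference fills much of the total and the ICC is low. If they differ widely, a large set-up difference can be hidden.

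With 0.75 as the sole rule for every parameter, a parameter with small differences could be declared not in agreement, and one with larger differences declared in agreement. The same set-ups could also give a different verdict in a sample with another spread.

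**Working it through.** **Inputs.** From the documents: the 0.75 cut-off, the absolute-agreement single-measures form, the eligibility ranges and the 2-SD exclusion. The documents give no expected ICC, between-person SD or error SD, so there is no planned figure to reproduce on this point. All SDs below are assumptions, in units of the random error SD.

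**Formulas.** Let sb be the between-person SD, b the mean ramp-treadmill difference and e the random error SD in each set-up. For two set-ups:

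- ICC (absolute agreement, single measures) = sb² / (sb² + b²/2 + e²)
- 95% limits of agreement = b ± 1.96 × √2 × e

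**Step 1: fix the disagreement, vary the spread (b = 0, e = 1).**

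| sb | ICC | Verdict at 0.75 | Limits of agreement |
|---|---|---|---|
| 1 | 1/2 = 0.50 | fail | ±2.77 |
| 1.5 | 2.25/3.25 = 0.69 | fail | ±2.77 |
| 2 | 4/5 = 0.80 | pass | ±2.77 |
| 3 | 9/10 = 0.90 | pass | ±2.77 |

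The flip point solves sb² = 0.75 × (sb² + 1), so sb² = 3 and sb = 1.73. With b = 1 it solves sb² = 0.75 × (sb² + 1.5), so sb² = 4.5 and sb = 2.12.

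**Step 2: fix the spread, vary the shift (sb = 2, e = 1).** For b = 0, 0.5, 1, 2, 3 and 4 the ICC is 0.80, 0.78, 0.73, 0.57, 0.42 and 0.31. A consistency ICC would stay at 0.80 throughout. The chosen form therefore does penalise a mean shift.

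**Step 3: the ranking can reverse.** With sb = 4, e = 1, b = 2, the ICC is 16/(16 + 2 + 1) = 0.84, a pass, with limits from −0.77 to 4.77. With sb = 1.5, e = 1, b = 0, it is 0.69, a fail, with limits of ±2.77. The worse-agreeing parameter is the one accepted.

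**Step 4: how this sample could move the ICC.**

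- Downwards: truncating a normal variable at 2 SD leaves 0.774 of its variance. If a participant is dropped when the value in either set-up is beyond 2 SD, simulation (one million participants, b = 0) takes a true ICC of 0.80 to 0.74 and one of 0.75 to 0.68. This assumes that the rule is applied to each outcome.
- Upwards: first peak load (N) and the loading rates (N/s) in Table 1 are not scaled to body mass. At equal height the BMI range allows a weight ratio of 29.99/18.5 = 1.62, so body size alone could raise the ICC for these outcomes.

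**Step 5: what the companion statistics add.** The paired t-test addresses b only. With more individual scatter it is less likely to be significant. The SEM depends on how it is computed. Take sb = 2, e = 1, b = 2, so the total variance is 4 + 2 + 1 = 7 and the ICC is 4/7. Total SD × √(1 − ICC) is then √(7 × 3/7) = √3 = 1.73, which mixes shift with scatter. From the residual mean square, the SEM is SD of differences/√2 = 1.41/1.41 = 1.00, which is scatter only. The plan does not say which is meant, and neither form enters the decision.

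**The case against.** A reader might infer that the verdict depends only on participant spread and not on how far the set-ups differ. The documents do not support that. The plan asks for absolute agreement, so the mean shift and the random disagreement are both in the denominator, as Step 2 shows. A reader might also infer that the sample was made homogeneous on purpose, or that frontal and transverse ranges have low spread. The documents state no such purpose and give no SD for any parameter. Step 4 shows that some outcomes may have wide spread.

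The best defence goes further. The information needed is nearly all in the plan already: the t-test requires the mean and SD of the paired differences, and a residual-based SEM gives the limits of agreement directly as mean difference ± 1.96 × √2 × SEM. The t-test is also not weak: with n = 25, e = 1 and b = 1 its power is about 92%, although it is about 40% at b = 0.5. The aim is tertiary and exploratory, no primary or secondary comparison uses the ramp, and the protocol limits its findings to healthy young adults. Finally, limits of agreement with no acceptable difference decide nothing.

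Most of this stands and keeps the point modest. It does not remove it: the only stated decision rule is the ICC cut-off, and nothing in the plan requires the difference to be reported or judged in outcome units. The last objection has to be met in the remedy.

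**Conclusion.** The concern holds in this form: the rule judges the set-up difference relative to participant spread, and the plan sets no limit on the difference itself. Under the assumed error SD of 1 and no shift, the ICC runs from 0.50 to 0.90 as the between-person SD goes from 1 to 3, crossing 0.75 at 1.73, with unchanged limits of ±2.77. These are illustrations. Without SDs in the documents, nobody can say which Table 1 parameter would be misjudged, or in which direction.

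This is a worthwhile, inexpensive improvement to an exploratory aim. It does not affect the primary or secondary hypotheses.

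**What to change.** In Statistical analysis, for each Table 1 parameter under the tertiary hypotheses and each of the four ramp-treadmill comparisons:

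- report the mean difference with its 95% CI and the Bland-Altman 95% limits of agreement in the parameter's own units, from the paired differences that the t-test already uses;
- define the SEM as the standard error of measurement from the residual mean square (SD of differences/√2).

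Reword the tertiary hypotheses so that an ICC of at least 0.75 is reported as relative reliability. Base any statement of agreement on the limits of agreement set against an acceptable difference that the sponsor fixes before analysis. Where none is fixed, report the limits descriptively, with no pass/fail verdict.

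The cost is a wording change and a few lines of script. No new data, participants or visits are needed. The downside is a longer table, at most 48 parameters × 4 comparisons = 192 rows, and a less simple pass/fail statement.

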## Dissemination of results and publication policy

A manuscript will be submitted to a journal with peer review process (e.g. Gait & Posture) aiming for an open access publication. Coded raw data will be made available upon request and for non-commercial purposes after publication of the results.

## Timeline of the project

---

Nov 2020	Submission to the local ethical committee (Medical University of Vienna)
Dec 2020	Ethical approval obtained
Jan 2021	Recruitment
Jan – Apr 2021	Field work
Mar – May 2021	Data analysis
May – June 2021	Finalization of manuscripts

## **Limitations and problems anticipated**

The condition speed-matched walking cannot be included into the randomization procedure. Due to the nature of the studied conditions, it will neither be possible to conceal the allocation, nor to blind participants or researchers. Another limitation is that different force plates are used for ramp-walking and treadmill walking, as well as the continuous quality of declined treadmill force plate data cannot be guaranteed. Thereby a small systematic error can maybe affect the kinetic outcome. Findings of this study will apply only to healthy young adults.

## **Conflict of interest and funding information**

The study team has no financial or academic conflict of interest to declare. No external funding will be requested.

